NCT Number:	NCT03651076
Official Title:	Randomized controlled trial of panniculus retraction methods for cesarean delivery
Document Type:	Study Protocol, including Informed Consent
Document Date:	11/9/2023

PART B STUDY DESCRIPTION

	Randomized controlled trial of panniculus retraction methods for cesarean delivery
Principal Investigator	[name], MD

B1. PURPOSE OF PROTOCOL

Our following three aims will test the central hypothesis that the use of the self-retaining panniculus retraction device (traxi®) will improve operative outcomes, as well as provider and patient satisfaction, for obese patients undergoing planned cesarean delivery.

AIM 1. Determine whether the use of traxi decreases surgical times in obese patients requiring panniculus retraction. We know from the available literature that surgical times, both from incision to delivery and incision to closure, in cesarean deliveries are longer in obese patients than non-obese patients. We hypothesize that the use of traxi will decrease surgical time.

AIM 2. Determine whether the use of traxi improves cardiopulmonary function in obese patients undergoing cesarean delivery. Vital capacity has been shown to be drastically reduced in obese pregnant patients, as compared to non-obese pregnant patients. We hypothesize that the use of traxi will improve pulmonary function testing and oxygen saturation obtained intraoperatively.

AIM 3. Determine whether that the use of traxi improves patient-reported and provider-reported experience. We hypothesize that the use of traxi will improve patient satisfaction due to maintenance of dignity and overall improved delivery experience. We postulate that provider satisfaction will improve due to facilitated visualization and easier cesarean delivery.

B2. SIGNIFICANCE AND BACKGROUND FOR THE STUDY

Introduction

Obesity rates have reached an all-time high in the general U.S. population. Currently, it is estimated that 25.6% of pregnant people have a BMI >30 and are considered obese [1]. Studies have shown that obese pregnant people are at higher risk for cesarean delivery and that their risk increases proportionately with increased BMI [2]. From a provider perspective, performing a cesarean delivery on an obese individual can be more technically challenging given the need for panniculus retraction to facilitate visualization of vital anatomic structures and delivery of the infant. As a result, operative times can be longer and additional personnel may be required in the operating room to assist in the delivery [3]. In addition, vital capacity has been shown to be drastically reduced in obese pregnant patients, as compared to non-obese pregnant patients [5,6].

The traxi® panniculus retractor (Clinical Innovations, Murray, UT) is designed to reliably retract the panniculus during surgery, thereby reducing the need for extra personnel for retraction; improve visualization to decrease operating time; and improve patient satisfaction with the delivery experience by preserving patient dignity. While the producers of this device claim that traxi is associated with these improved outcomes, no clinical trials exist to support these claims. A single clinical trial was initiated but was terminated due to low enrollment with only four subjects [7]. Given the absence of primary data in support of this device, we propose this clinical trial to examine traxi's utility and potential benefits to this patient population.

References

- Chu, S. Y., Kim, S. Y., Schmid, C. H., Dietz, P. M., Callaghan, W. M., Lau, J. and Curtis, K. M. (2007), Maternal obesity and risk of cesarean delivery: a meta-analysis. Obesity Reviews, 8: 385–394.
- 4. Poobalan, A. S., Aucott, L. S., Gurung, T., Smith, W. C. S. and Bhattacharya, S. (2009), Obesity as an independent risk factor for elective and emergency caesarean delivery in nulliparous women systematic review and meta-analysis of cohort studies. Obesity Reviews, 10: 28–35.
- 6. von Ungern-Sternberg, Effect of obesity and site of surgery on perioperative lung volumes. British Journal of Anaesthesia , Volume 92 , Issue 2 , 202 207.
- 7. https://clinicaltrials.gov/ct2/show/NCT02865083?term=pannus+retraction&rank=1

B3. DESCRIPTION OF RESEARCH PROTOCOL A. Study Design – Overview, Methods, Procedures

Overview

To determine whether the traxi® device warrants incorporation into routine practice, we will conduct an open-label, randomized, controlled trial to evaluate the use of traxi for obese patients undergoing non-urgent cesarean delivery. We will examine operative time, cardiopulmonary function, and patient/provider satisfaction.

Methods

Enrollment/randomization

Screening, recruitment, and enrollment of participants will occur in the obstetrical clinics and on Labor and Delivery at Brigham and Woman's Hospital (BWH), Beth Israel Deaconess Medical Center (BIDMC) and at Massachusetts General Hospital (MGH). Possible eligible patients may be handed a brochure about the study by their OBGYN provider at BIDMC so they can decide make an informed choice about participating. We will review the medical record of potentially eligible patients to confirm eligibility. At the time we approach each patient, we will review the eligibility criteria with the patient to further ensure eligibility. A script is available for the consenter. Specifically, consistent with standard medical care, we will confirm with patients that they do not have a history of allergic reaction to adhesives, such as those used in medical tape.

Participants who meet eligibility criteria and provide written, informed consent will be randomized to the traxi arm or standard of care (control) arm. We will use computer-generated block randomization to randomize participants in a 1:1 ratio to the traxi arm or the control arm. Randomization will be stratified by whether the patient has a history of cesarean delivery / open abdominal surgery versus no history of cesarean delivery / open abdominal surgery versus no history of cesarean delivery.

Study procedures

After the participant is in the operating room and before the cesarean delivery, we will use a spirometer to measure forced vital capacity, forced expiratory volume, vital capacity and tidal volume. We will perform these measurements while the participant is in the supine position both before any retraction has occurred and after the traxi device or standard method for panniculus retraction has been applied.

After the cesarean delivery is complete, we will assess provider satisfaction by administering a brief questionnaire developed by our research team. The survey will be distributed to personnel involved in

the delivery either on paper or via REDCap.

We will assess participant satisfaction via a survey that will be available either on paper or via REDCap.

We will conduct a medical record review to collect data on the secondary outcomes below that are not available via spirometry or questionnaire.

Outcomes

The primary outcome will be total operative time, time from incision to closure.

Secondary outcomes will include:

- Spirometry: forced vital capacity, forced expiratory volume, vital capacity and tidal volume
- Provider satisfaction
- Participant satisfaction
- Intraoperative data, such as estimated blood loss and number of scrubbed personnel
- Neonatal outcomes, such as Apgar score and NICU admission
- Length of stay postoperatively,
- Maternal complications, such as need for re-admission and wound disruption or infection.

B. Statistical Considerations

Sample Size Justification: Our sample size calculation is based on data from a prior study that reported total operative time (incision to closure) by BMI [7]. In that study, for patients with a BMI \geq 40 the mean total operative time was 55.0 minutes (±26 minutes). We hypothesize that the operative time in the control arm will be similar to that in the prior study and that the mean operative time in the traxi arm will be 45 minutes (±10 minutes). Using a two-sided alpha of 0.05, in order to achieve 85% power to detect the specified difference we will need 102 participants per arm. To allow for 15% loss to follow-up, we will aim to enroll 120 participants per arm.

We hypothesize that participants will have a baseline forced vital capacity of 2.0L and that after retraction the forced vital capacity will drop by 0.1L to 1.9L in the control am. Assuming a two-sided alpha of 0.05, we will have more than 85% power to detect a difference between the 0.1L decrease in the control arm and a 0.19 L decrease in the traxi arm (assuming a standard deviation of the difference of 0.2L).

Data Analysis: We will employ an intention-to-treat approach for the data analysis. Descriptive data will be presented as a proportion, mean with standard deviation or median with interquartile range. Comparisons will be made using Chi-square or Fisher's exact test for categorical variables and parametric or non-parametric tests for continuous variables based on data distribution.

We will use linear regression to estimate beta and 95% confidence intervals for difference in the primary outcome, time from incision to closure, between the traxi and control arms. While we anticipate that randomization will balance the distribution of measured and unmeasured potential confounders in the two study arms, if this is not the case, we will assess the influence of potential confounders as needed. We will use a similar analytic approach for the secondary outcomes, which also are continuous. All data will be analyzed with SAS 9.4 (SAS Institute Inc., Cary, NC, USA). All tests will be two sided and a P value <0.05 will be required to confer significance.

Release of Data

Data from study participants enrolled at BWH and MGH will be sent to BIDMC, the coordinating site. A data use agreement will be executed to facilitate data transfer. Data will be sent via secure data transfer.

The PI will create a research steering committee that includes the PI and at least one other coinvestigator. All requests to use data from the study must be made in writing and will be reviewed by the steering committee. Release of data may occur after appropriate data use agreements have been enacted.

Investigators can request to use 1) data that contain elements of a limited dataset or 2) data that are completely de-identified. Investigators who wish to obtain data that contain elements of a limited dataset first must obtain approval from the steering committee and then will have to obtain appropriate approval from the BIDMC Committee on Clinical Investigations (CCI) and from their own institution. After obtaining approval, data may be given to the researchers. Investigators who wish to receive completely de-identified data may do so after approval by the steering committee and after signing a letter indicating that they will not attempt to obtain the identity of any of the participants. A data use agreement or material transfer agreement will be executed as needed.

C. Subject Selection

Inclusion criteria for patients

- Pregnant
- Age 18-50 years
- BMI greater than or equal to 40 kg/m²
- Undergoing non-emergent cesarean delivery
- Able and willing to provide written, informed consent
- Singleton gestation

Inclusion criteria for providers

- Listed as a provider_on the patient's delivery summary
- May include nurse, resident, attending, medical student, anesthesiologist, physician's assistant, surgical technician

Exclusion criteria for patients

- Fetal demise
- Disruption of abdominal skin, such as due to infection, rash, abrasion or laceration
- Known adhesive allergy

B4. POSSIBLE BENEFITS

We do not know whether participants in the study will gain any direct benefit from participation. However, we hope that this study will provide data to inform how we can improve care for future patients. It is possible that participants who are randomized to the intervention arm of this study will have a better delivery experience due to increased preservation of dignity. It also is possible that providers will benefit by improving retraction capability and thus visualization while operating and operative efficiency.

B5. POSSIBLE RISKS AND ANALYSIS OF RISK/BENEFIT RATIO

There are very few anticipated risks involved in this study. Patients with an allergy to adhesives may experience a contact dermatitis allergic reaction to the adhesive of the traxi device or the medical tape.

Additional risks are largely psychosocial. Obesity can be a difficult topic to navigate with patients. As this device is used only in obese patients, some patients may feel uncomfortable when approached for this study. Study staff will be sensitive to this issue when approaching patients for enrollment.

To protect patient privacy and prevent a breach of confidentiality, all data will be handled in a confidential manner. We will use REDCap, a HIPAA-compliant, web-based data collection tool to securely store all data.

B6. RECRUITMENT AND CONSENT PROCEDURES

Recruitment

At BIDMC and MGH, study staff will review the cesarean delivery schedule and the census on Labor and Delivery to identify patients who may be eligible for the study. To the extent possible, eligibility will be confirmed by reviewing the medical record before the patient is approached. The study staff also will confer with the one of the patient's clinicians to ensure that it is okay to approach the patient about the study. Possibly eligible patients will be handed a brochure by their providers. They may also see the brochure in the OBGYN department and choose to read about it on their own. Patients will be approached on Labor and Delivery in a private space and clinic visits.

In addition, BWH permits study staff to call and email patients for study recruitment. Thus, BWH study staff will approach potentially eligible BWH patients via phone and email, in addition to using the inperson recruitment described above.

Providers who participated in the delivery will be sent an email to ask to participate in a REDCap survey on provider experience. Providers will be identified by looking at the list of providers in the patient's delivery summary.

Consent

Members of the study team will obtain written informed consent from participants when they are in a private clinical space. The participant will be provided with a copy of the informed consent. A script is available for use during enrollment. Providers will be consented in the email communication. The email contains required consent elements so that the providers can be well informed about participation, and they will opt in by responding to the survey.

Subject Protection

We do not believe that pregnant patients are vulnerable. Nonetheless, patients approached will be assured that their participation is completely voluntary and will not affect their clinical care. Participation in the provider survey is voluntary.

B7. STUDY LOCATION

Privacy

We will obtain consent in a private clinical setting at the hospital, and surveys will be administered to participants in a private post-partum or OBGYN exam room.

Physical Setting

Study activities will take place at BIDMC, Brigham and Women's Hospital (BWH) and at Massachusetts General Hospital (MGH).

B8. DATA SECURITY

All electronic data will be kept in a restricted-access folder on the BIDMC or MGH secure server, behind the firewall. Any paper resulting from this study will be kept in a locked office belonging to a member of the study staff. We will use REDCap, a HIPAA compliant, web-based collection tool to securely store all data.

B9 Multi-Site Studies

Is the BIDMC PI the lead investigator of the multi-site study? Yes No We are planning to have at minimum a quarterly conference call with the traxi personnel at BWH and MGH to discuss anything about the study. We may have more frequent calls to discuss changes and important updates if necessary. If unanticipated problems, adverse events and/or noncompliance arise, we plan to follow BIDMC/CCI post-approval reportable event guidelines to report these issues. We are working closely with MGH personnel to ensure that they will submit and follow a protocol similar to the one we do. Changes made to the protocol by BWH and MGH must also be approved by us. These amendments can be discussed in conference calls.

B10 Dissemination of Research Results

We will not provide research results directly to participants. Aggregate results will be presented via poster, oral presentation and manuscript.

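### Three hospitals enroll, but the primary regression names neither hospital nor the surgical-history stratum, so any between-hospital variance in operative time widens the confidence interval

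*Combined protocol and SAP*

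**What the plan says.** Sections B3.A (Enrollment/randomization) and B7 place recruitment and study activities at BWH, BIDMC and MGH.

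On allocation, section B3.A says: "We will use computer-generated block randomization to randomize participants in a 1:1 ratio to the traxi arm or the control arm". The strata are given next: "Randomization will be stratified by whether the patient has a history of cesarean delivery / open abdominal surgery". Hospital is not listed as a stratum, and no separate list per hospital is described.

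On the outcome, section B3.A says: "The primary outcome will be total operative time, time from incision to closure".

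On the analysis, section B3.B (Data Analysis) says: "We will use linear regression to estimate beta and 95% confidence intervals for difference in the primary outcome". The comparison is between the two arms, and no covariate is named. The section expects randomization to balance potential confounders and provides for looking at their influence only if it does not. No variable, threshold or model is attached to that provision. A similar approach is planned for the secondary outcomes.

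**The concern.** Incision-to-closure time depends on who operates and how, so hospital is a plausible predictor of it. The control arm is standard retraction, which the protocol does not define further.

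If hospital does predict the outcome, the plan uses that information neither in the allocation nor in the planned model. The between-hospital part of the variance then counts as unexplained noise. The interval for the treatment difference is wider than it needs to be, and power is lower than the same patients could give.

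The conditional clause on confounders does not repair this. Between-hospital variance sits in the residual even when the arms are perfectly balanced on hospital, so a rule triggered by imbalance cannot be relied on to recover the precision. The clause also leaves the choice between adjusted and unadjusted results open until the data are seen, in an open-label trial.

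The surgical-history factor has the same gap: it is used to stratify and is then not named in the model.

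**Working it through.** **Inputs from section B3.B (Sample Size Justification).** Control 55.0 minutes, SD 26; traxi 45 minutes, SD 10; difference 10 minutes; two-sided alpha 0.05; 85% power; 102 per arm, raised to 120 for 15% loss.

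**The plan's own figure.**
- n per arm = (z₀.₉₇₅ + z₀.₈₅)² × (26² + 10²) / 10² = (1.960 + 1.036)² × 776 / 100 ≈ 69.7, so 70, not 102.
- With the stated SDs, 102 per arm gives 95.2% power.
- A common SD of 26 would need 122 per arm. An SD of about 23.8 in both arms is what makes 102 match 85% power.
- The loss step does reproduce: 102 / 0.85 = 120.

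The mismatch is a separate matter and does not affect this point. It does mean that power should be shown for more than one SD.

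**Standard error without hospital in the model.** Average within-arm variance = (676 + 100) / 2 = 388 min². SE = √(2 × 388 / 102) = 2.76 minutes.

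**Standard error with hospital in the model.** The between-hospital variance is assumed, and 388 is taken as the total including it.

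- *Hospital means at -5, 0 and +5 minutes, three equal hospitals.* Between-hospital variance = 2 × 5² / 3 = 16.7 min², or 4.3% of 388. SE = √(2 × (388 - 16.7) / 102) = 2.70 minutes, about 2% smaller.
- *Hospital explains a share r of the variance.* SE = √(2 × 388 × (1 - r) / 102):

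| r | SE (min) | Power, stated SDs | Power, SD 23.8 | Power, SD 26 in both arms |
|---|---|---|---|---|
| 0 | 2.76 | 95.2% | 85.0% | 78.4% |
| 0.05 | 2.69 | 96.1% | 86.7% | 80.5% |
| 0.10 | 2.62 | 96.9% | 88.5% | 82.5% |
| 0.15 | 2.54 | 97.6% | 90.1% | 84.6% |

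The SE column uses the stated SDs; the last two columns apply the same 1 - r reduction to a larger SD.

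**Chance imbalance is not an additional harm.** At -5, 0 and +5 minutes, the shift in the arm difference from uneven hospital mix has SD √(2 × 16.7 / 102) = 0.57 minutes. That is the gap between the two standard errors: 2.758² - 2.698² ≈ 0.33 = 0.57². The unadjusted interval already contains it.

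**Small offset.** If allocation ignores hospital, estimating two hospital terms costs roughly 2/204 ≈ 1% of variance, or about 0.5% of the SE (0.01 minutes). The figures above leave this out. If hospital explained less than about 1% of the variance, there would be no net gain.

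**The case against.** The strongest reply is that nothing here is invalid and the gain may be slight. Randomization protects the unadjusted comparison. With the stated SDs, power is already 95.2%, and even r = 0.15 adds only 2.4 points. Gains approach 6 points only if the SD is larger than stated. The protocol reports no difference between hospitals at all. All of this stands, and it limits the size of the point.

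It can also be said that the confounder clause could bring hospital in. It could, but only after the data are seen and only on imbalance, so it does not secure the precision. Separate lists per hospital may also be in use without being described. The model term would still be wanted then, because leaving out a factor that was balanced by design makes the standard error too large when that factor predicts the outcome.

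A reader might go further in four ways that the protocol does not support:
- *Each hospital has its own control method.* The protocol refers only to a standard method and nowhere says that it differs by hospital.
- *Very large hospital effects.* Means at -15, 0 and +15 minutes imply a between-hospital variance of 2 × 15² / 3 = 150 min², above the whole variance assumed for the traxi arm (10² = 100 min²).
- *Uneven splits as a second problem.* With 80 patients per hospital and 120 per arm, the chance that at least one hospital splits 45:35 or worse is about 43%. This is the same component of the standard error seen from another side.
- *Hospitals free to go their own way.* Section B9 does ask of MGH only to "ensure that they will submit and follow a protocol similar to the one we do", but it also requires the coordinating site to approve changes and sets at least quarterly calls. The hospital question gives no ground for rewriting that section or changing the block sizes.

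**Conclusion.** The omission is certain: hospital is neither a stated stratum nor a stated model term, and the stratification factor is missing from the model too. The consequence is avoidable loss of precision, not bias, and it is probably modest. At 102 per arm and the stated SDs, the standard error falls from 2.76 minutes to about 2.70 with hospital means 5 minutes apart, and to 2.54 if hospital explains 15% of the variance.

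These sizes rest on an assumed between-hospital variance, on equal hospital sizes in the first case, and on reading the stated SDs as total variation. The protocol does not show whether the SD of 26, taken from a prior study, already includes differences between hospitals. The change is worth making because it costs almost nothing and settles the primary model before the data are seen.

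**What to change.** In section B3.B (Data Analysis), state that the primary regression of incision-to-closure time contains treatment arm, hospital (three levels) and the surgical-history stratum as fixed effects, whether or not imbalance is observed. Apply the same terms to the regressions for continuous secondary outcomes. Define the surgical-history term with the levels actually used in the randomization, because the printed sentence lists an overlapping third level.

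If enrollment has begun, leave the allocation list unchanged; the model terms alone recover most of the precision.

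Cost: one or two sentences and about 3 degrees of freedom out of about 200 (two for hospital, one for a two-level surgical history). No extra patients or procedures are needed.

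### Spirometry is taken before and after retraction, but the analysis text names neither the dependent variable (change or post-retraction value) nor adjustment for the pre-retraction value

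*Combined protocol and SAP*

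**What the plan says.** Section B3.A (Study procedures) schedules spirometry with the participant supine, "both before any retraction has occurred and after the traxi device or standard method for panniculus retraction has been applied". The outcome list in the same section gives "Spirometry: forced vital capacity, forced expiratory volume, vital capacity and tidal volume" and does not say whether change or the post-retraction value is meant.

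Section B3.B (Statistical Considerations) includes a power statement for FVC. It starts from a "baseline forced vital capacity of 2.0L" and compares "a difference between the 0.1L decrease in the control arm and a 0.19 L decrease in the traxi arm", with a standard deviation of the difference of 0.2 L. The claim reads "Assuming a two-sided alpha of 0.05, we will have more than 85% power to detect a difference".

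The Data Analysis text in B3.B first offers general two-group tests, parametric or not according to the distribution. It then specifies linear regression for operative time and adds: "We will use a similar analytic approach for the secondary outcomes, which also are continuous". On covariates, it expects randomization to balance confounders and says "if this is not the case, we will assess the influence of potential confounders as needed".

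Section B3.A (Enrollment/randomization) also states: "Randomization will be stratified by whether the patient has a history of cesarean delivery / open abdominal surgery".

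**The concern.** The regression that the secondary outcomes inherit was written for operative time, which has no baseline value. Carried over literally to spirometry, it could mean a regression of change on arm or a regression of the post-retraction value on arm. The power paragraph points to change for FVC, but nothing does so for the other three measures, and the analysis text does not repeat it. The inherited sentence also describes the secondary outcomes as continuous, although the list includes NICU admission and re-admission. It was evidently not written outcome by outcome.

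The pre-retraction value is not prespecified as a covariate anywhere. The only adjustment foreseen depends on imbalance seen in the data and names no variable and no trigger. The main reason to adjust for a baseline measurement is precision, and that reason applies whether or not the arms happen to be balanced.

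Three things are at stake: whether the power statement describes the analysis that is run, some precision available at no cost, and a modelling choice left open until the baseline data have been seen. Spirometry is central to Aim 2, and FVC is the only secondary outcome with a power statement.

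**Working it through.** **Inputs from the protocol (B3.B).** Decreases of 0.10 L and 0.19 L, so an absolute difference of 0.09 L. SD of the difference 0.2 L, read as the SD of within-patient change. Two-sided alpha 0.05. 102 per arm evaluable and 120 per arm enrolled (102/0.85 = 120).

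**Assumption, not in the documents.** Between-patient FVC SD, S, equal before and after retraction, ranging from 0.2 to 0.6 L.

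**Step 1: the plan's own figure.** For a change-score comparison at 102 per arm, SE = 0.2 × √(2/102) = 0.0280, and 0.09/0.0280 = 3.21. The normal approximation gives Φ(3.21 − 1.96) = 0.895; the noncentral t gives 0.892. At 120 per arm the noncentral t gives 0.935. About 90 per arm would give 85%. The claim of more than 85% therefore reproduces if change is analysed.

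**Step 2: the three candidate analyses.** With equal SDs, the variance of change is 2S²(1 − ρ). Setting this to 0.2² = 0.04 gives ρ = 1 − 0.04/(2S²). The residual SD is then:
- change: 0.2 L
- post-retraction value only: S
- post-retraction value adjusted for pre-retraction value: S√(1 − ρ²), which equals 0.2 × √((1 + ρ)/2)

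Example at S = 0.4: ρ = 1 − 0.04/0.32 = 0.875, and the adjusted residual SD is 0.4 × √(1 − 0.766) = 0.194.

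**Step 3: power at 102 per arm (noncentral t).**

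| S (L) | ρ | Adjusted SD (L) | Change | Adjusted | Post only |
|---|---|---|---|---|---|
| 0.20 | 0.50 | 0.173 | 89% | 96% | 89% |
| 0.25 | 0.68 | 0.183 | 89% | 94% | 73% |
| 0.30 | 0.778 | 0.189 | 89% | 92% | 57% |
| 0.40 | 0.875 | 0.194 | 89% | 91% | 36% |
| 0.50 | 0.92 | 0.196 | 89% | 90% | 25% |
| 0.60 | 0.944 | 0.197 | 89% | 90% | 19% |

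The variance ratio of adjusted to change is (1 + ρ)/2. Variance is therefore 25% lower at S = 0.2 L, and 11%, 6%, 4% and 3% lower at 0.3, 0.4, 0.5 and 0.6 L. For that last range the standard error is 6%, 3%, 2% and 1% lower. At 120 per arm, adjusted power is 96%, 95%, 94% and 94% at 0.3–0.6 L, against 93% for change.

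Post-only power drops below 85% once S exceeds about 0.21 L, and below half the change-score power once S exceeds about 0.35 L.

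**Step 4: would adjustment only on imbalance rescue a post-only analysis?** The plan names no trigger, so this is illustrative. Assume adjustment only when the baseline t-test has p < 0.05. In 8,000 simulated trials per SD at 102 per arm, adjustment was triggered in 5.0–5.4% of trials. Power was 59%, 39%, 27% and 21% at S = 0.3, 0.4, 0.5 and 0.6 L, little better than no adjustment.

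**The case against.** The strongest reply is that the protocol largely settles FVC already. The power paragraph sits in the same section as the analysis text and states the comparison as a difference in decreases, and the paired measurements exist to permit it. On that reading the gap is a missing cross-reference, the stated power is met, and adjustment adds only about 1–3 percentage points at S = 0.3–0.6 L. The large losses need both the less natural post-only reading and an SD that the documents do not give. The two benefits do not add up either, since the gain over change is smallest where the post-only loss is largest. Change and adjusted analyses are both unbiased under randomization, so the choice between them is one of efficiency. The simulated trigger is not a rule in this plan.

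Most of this stands as a limit on size, and the post-only and trigger figures should be read as conditional. It does not close the gap. A power assumption is not an analysis specification, and this one covers FVC only. The forced expiratory volume, vital capacity and tidal volume analyses remain undefined, and baseline adjustment is prespecified nowhere. Writing only that change will be analysed would remove the ambiguity, but it would forgo precision that costs nothing.

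**Conclusion.** The concern holds. The analysis text does not define the spirometry dependent variable and does not prespecify adjustment for a pre-retraction value that every participant is scheduled to provide.

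On the natural reading (change), the effect is modest: power rises from 89% to 90–92% at 102 per arm for an assumed SD of 0.3–0.6 L, and to 96% at 0.2 L. On the post-only reading, the claim of more than 85% power would fail for any SD above about 0.21 L. These figures rest on the protocol's 0.09 L difference and 0.2 L SD of change, and on the assumption of equal SDs before and after retraction.

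The ranking of the methods does not need that last assumption. The adjusted model estimates the weight given to the pre-retraction value, whereas change fixes it at 1 and post-only fixes it at 0. In large samples the adjusted model is therefore at least as precise as either. The matter is worth correcting because the cost is so low, but it affects a secondary outcome and leaves the primary analysis and sample size untouched.

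**What to change.** Add to the Data Analysis text: *Each spirometry outcome (forced vital capacity, forced expiratory volume, vital capacity, tidal volume) will be analysed by linear regression of the post-retraction value on arm, adjusted for the participant's own pre-retraction value and the randomization stratum, regardless of observed imbalance.*

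State that the FVC power calculation refers to this model. Keeping 0.2 L as the SD is conservative, because the adjusted residual SD in large samples cannot exceed the SD of change. No correlation then has to be assumed.

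The stratum term only mirrors the stratified randomization, and no gain is claimed for it here. The sentence that defines the strata repeats its no-history category, so it should be clarified before the stratum is used as a covariate.

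The cost is one sentence and a named covariate list. No new data, no change for participants and no change in sample size are needed.
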